10.4 Dates of First and Last Dose of Study Drug

The date of first dose of IMP will be the first dose date recorded on the Study Drug page of the CRF. The date of the first dose of IMP in the Extension Phase, will be the first dose date on the Study Drug Administration (Extension Phase) page of the CRF.

If no date of first dose of IMP is available and the subject was not treated, date of first dose of IMP will be missing and the date of randomization will be used in any calculations requiring treatment start date.

Date of last dose of IMP will be the date collected as the completion/discontinuation date on the End of Treatment page of the CRF. If date of last dose of IMP is not available and subject is lost to follow-up based on End of Treatment CRF page, date of last scheduled visit or date of last telephone contact where a dose is recorded, will be used as the date of last dose of IMP.

Subjects who entered the Extension Phase under protocol versions 1.0 to 4.0 will have no End of Treatment page completed after completion of the randomized part. For these subjects, date of the last dose of IMP in the randomized part will be the day prior to the date of the first dose of IMP in the Extension Phase.

10.5 Actual Treatment

To determine the actual treatment in the study for the purpose of safety analysis, subjects will have actual treatment assigned as the dose the subject first received regardless of any dispensing issues at a later visit. For example, if a subject was randomized to placebo but the subjects first dispensed dose in the study was active treatment, they will be assigned actual treatment as the active arm they first received, even if they were later dispensed placebo at all remaining visits.

For subjects entered in the Extension Phase under protocol versions 1.0.to 4.0, subjects on placebo will have actual arm in the Extension Phase set to the active dose they first receive in the extension phase regardless of the active dose they were randomized to. Subjects in the active arm, will remain assigned the actual treatment in the Extension Phase they first had dispensed.

10.6 Prior and Concomitant Medications

Prior medications will be defined as those medications which started prior to the first administration of study drug.

Concomitant medications will be defined as medications starting prior to but ongoing after first administration of IMP or with a start date on or after first dose of IMP in the randomized part.

Concomitant medications for the Extension Phase will be defined as medications starting prior to but ongoing after first administration of IMP in the Extension Phase or with a start date on or after first dose of IMP in the Extension Phase.

Medications which start prior to the first dose of IMP and are ongoing at the time of first dose of IMP will be summarized as both prior and concomitant medications.

Sponsor: Calliditas Therapeutics Suisse SA

Protocol No: GSN000350

10.7 Adverse Events

10.7.1 Treatment Period

The analysis of safety assessments over the **24-week treatment period** (Week 24 + 30 days) will be conducted:

- For patients enrolled under protocol version 5.0 or later who complete the 24-week treatment period, a Week 28 (EoT) visit will occur 30 days after the date and time of last dose of IMP. All safety data will be analyzed.
- For patients enrolled under protocol versions 1.0 to 4.0, treatment may have continued beyond Week 24. Regardless, the safety data will be cut at Week 28 (Week 24 + 30 days) to ensure a consistent safety follow-up period for all patients.

This approach enables the evaluation of the safety and tolerability of setanaxib over a 24-week treatment period, consistent with the study objectives.

The analysis of safety assessments over the **52-week treatment period** (Week 52 + 30 days) will also be conducted:

- Patients enrolled under protocol version 5.0 will contribute safety data up to Week 28 only. All safety data will be analyzed.
- For patients enrolled under protocol versions 1.0 to 4.0 who complete the 52-week treatment period and do not enter the extension phase, a Week 56 (EoT) visit will occur 30 days after the date and time of last dose of IMP. All safety data will be analyzed.
- For patients enrolled under protocol versions 1.0 to 4.0 who entered the extension phase, the safety data will be cut at Week 56 (Week 52 + 30 days) to ensure a consistent safety follow-up period for all patients.

This approach enables the evaluation of the safety and tolerability of setanaxib over the whole randomized treatment period and provides longer-term safety information. This approach will be applied to other safety endpoints.

Note: For the analysis of study drug exposure and compliance (Section 12.3.3), the last dose of IMP in the 24-week treatment period will be cut at week 24, and the last dose in the 52-week treatment period (for subjects who received more than 24 weeks of treatment) will be cut at week 52. "+ 30 days" will not be considered in the drug exposure and compliance.

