Eligible patients will be randomized to oral setanaxib 1200 mg/day, 1600 mg/day, or placebo, according to a 1:1:1 randomization ratio, stratified by Screening serum ALP < or  $\geq$ 3.0×ULN. See Section 6.3 for further details on the method of assigning patients to the treatment groups, and see Section 6.4 for further details on the dose and administration of setanaxib and placebo.

Baseline assessments will be performed on Day 1 (Visit 3). Post-Baseline assessments will be performed at Weeks 2 (Visit 4), 4 (Visit 5), 8 (Visit 6), 12 (Visit 7), and 24 (Visit 8). In addition, study patients will be contacted by phone by the study site staff at Weeks 16 and 20.

Special Note: Patients who are following the previous protocol schedule (protocol version 4) and are already beyond Week 24 should permanently discontinue IMP as soon as possible and have an EoT Visit 30 days after their last dose.

Following permanent IMP discontinuation at any time during the study, patients will undergo an EoT Visit 30 days after their last dose. If IMP is permanently discontinued, the study assessments should continue until completion of the Week 24 Visit (Visit 8). If it is not feasible to complete all the visits, every possible effort should be made to complete the Week 24 Visit.

The Investigator, the site personnel, the Sponsor and their representatives involved in monitoring and conducting the study, and the patients will be blinded to treatment assignments until the database is locked and the study is unblinded for analysis (see Section 6.2). Also see Section 6.2 for details on access to the treatment codes in the event of emergency unblinding.

If applicable, patients will continue UDCA, OCA, and bezafibrate or fenofibrate treatment at a stable dose during the Double-blind Treatment Period. Patients should not start additional treatments for PBC after Randomization. All medications will be recorded in the electronic Case Report Form (eCRF).

Throughout the study, particular attention will be given to the detection and management of AESIs, suspected cases of DILI (see Section 5.3.2.1 and Appendix II), potential cases of bone marrow toxicity (see Section 5.3.2.2), and potential cases of hypothyroidism (see Section 5.3.2.3).

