8.1 Sample Size Considerations

The primary efficacy endpoint is the change in ALP (%) over 24 weeks. It is planned to enroll approximately 60 to 70 subjects. Subjects will be randomized and allocated to placebo, setanaxib 1200 mg/day, or setanaxib 1600 mg/day according to a 1:1:1 randomization ratio.

This study is designed to detect a >25% reduction in ALP in setanaxib-treated subjects versus a 2.5% reduction in the placebo arm with an overall 2-sided p<0.05. Standard deviations are assumed to be 19% and 24%, respectively, based on the Phase 2a study with setanaxib and the Phase 3 POISE study with Ocaliva. With approximately 16 evaluable subjects per arm (48 subjects overall) and using a Hochberg step-up procedure (Benjamin and Hochberg, 1995; Section 12.5.1 for details) to control alpha across 2 dose comparisons versus placebo, this study has 88.2% global power to detect at least 1 treatment arm as significantly different from placebo and 68.3% power to detect both treatment arms as statistically significant. Also, for the secondary endpoint of change in fatigue, there will be >80% power to detect a 20% (SD 20%) reduction in fatigue versus a 2.5% (23%) increase in the placebo arm.

An assumed dropout rate of approximately 25% leads to a target sample size of 66 enrolled subjects (22 per arm). A range of approximately 60 to 70 enrolled subjects allows for variability in the assumed dropout rate.

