9.6.2 Safety Analysis Set

The safety analysis set (SS) will include all randomized subjects who receive at least 1 tablet of IMP or placebo. Subjects included will be analyzed based on actual treatment initially received.

Safety data collected from subjects who entered the extension phase will be listed only.

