10.7.2 Treatment-Emergent Adverse Events (TEAE)

The treatment emergent period will be defined in two ways:

(1) **TEAEs over a 24-week treatment period** will be defined as AEs that occur, having been absent before the date and time of the first dose of the IMP, or have worsened in severity or seriousness after initiating the IMP until Week 28 (Week 24 + 30 days) in the **24-week treatment period**.

For patients enrolled under protocol versions 1.0 to 4.0, the AEs that occur, or have worsened in severity or seriousness after Week 28 (Week 24 + 30 days) will NOT be taken into consideration in TEAEs over a 24-week treatment period.

(2) TEAEs over a 52-week treatment period will be defined as AEs that occur, having been absent before the date and time of the first dose of the IMP, or have worsened in severity or seriousness after initiating the IMP until Week 56 (Week 52 + 30 days) in the **52-week treatment period**.

For patients enrolled under protocol versions 1.0 to 4.0 who entered the extension phase, the AEs that occur, or have worsened in severity or seriousness after Week 56 (Week 52 + 30 days) will NOT be taken into consideration in TEAEs over a 52-week treatment period.

TEAEs will be assigned to the Extension Phase based on AE start date:

Version Date: 27-June-2024

Sponsor: Calliditas Therapeutics Suisse SA

Protocol No: GSN000350

 If the start date of the TEAE is on or after the first dose in the Extension Phase, the TEAE will be assigned to the Extension Phase.

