10.11 PROMIS-Short Form-Fatigue 7b Daily

The PROMIS-short form-Fatigue 7b Daily comprises of 7 questions asking the subject to evaluate their fatigue since waking up. Each of the questions on a 5-point scale (range 1-5) with a range of possible values for the score for the daily form from 7 to 35. Higher scores indicate worse functioning for fatigue. This measure will be completed at home by the subject via daily diary over 7 consecutive days prior to the study visits.

Total daily raw scores will be obtained by summing item scores, which are converted into T-scores standardized (mean=50, SD=10). The standardized T-score is reported as the final daily score for each participant. The daily raw scores will be converted into T-scores using the table in Appendix 3 (HealthMeasures, 2019). All questions must be answered in order to produce a valid score using the scoring tables, if the subject does not answer all 7 questions completely, the total daily raw scores are set to missing.

The T-scores for baseline and post-baseline visits will be calculated by averaging the daily T-scores before the visit date (inclusive). The calculation of this average value will proceed only if 4 or more daily T-scores are available; otherwise, the final score will be treated as missing for the corresponding visit. The baseline T score will be defined as the mean of the daily T scores over the last 7 days prior to first treatment administration. For post-baseline assessments only, if data over 8 days is collected, all 8 days will be included in the calculation of the average value.

Approximately 15 subjects will have no baseline value for the PROMIS-short form-Fatigue 7b Daily as they were enrolled under Protocol Version 1.0 and this questionnaire was not added until Protocol Version 2.0. These missing data will not be imputed for the main analysis.

Sponsor: Calliditas Therapeutics Suisse SA

Protocol No: GSN000350

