12.6 Safety Analyses

12.6.1 Adverse Events

All AEs will be coded using MedDRA Version 24.0 or later. All AEs (including non-treatment-emergent and post-treatment events) recorded on the CRF will be listed. AEs that are not treatment emergent will be flagged for both treatment emergent definitions described in Section 10.7.1 and AEs that are assigned to the extension phase will also be flagged. Only TEAEs (see Section 10.7.2) will be included in AE summary tabulations unless otherwise specified. Summary tables of TEAEs will be presented by treatment group and

Version Date: 27-June-2024

Sponsor: Calliditas Therapeutics Suisse SA

Protocol No: GSN000350

total for the SS and repeated for both treatment emergent definitions. The National Cancer Institute common terminology criteria for Adverse Events (CTCAE) toxicity grading criteria version 4.03 will be used for toxicity grading of AEs.

All AE summaries will include the number and percentage of subjects in each category and the number of events. For the calculation of the incidence of events, subjects will only be counted once within the events. For summaries by SOC and PT, subjects will be counted once per unique PT and SOC. For summaries by SOC and PT tables should be sorted in descending order of SOC and then PT by subject counts in the total group.

An overall summary of TEAEs will be presented with the following categories:

- Any TEAEs
 - TEAEs related to IMP
- Any severe TEAEs (CTCAE Grade 3 or greater)
 - o Any severe TEAEs (CTCAE Grade 3 or greater) related to IMP
- Any TESAEs
 - Any TESAES related to IMP
- TEAEs with outcome of death (events with outcome of Fatal on the AE CRF page)
 - o TEAEs related to IMP with outcome of death
- TEAEs leading to discontinuation of study treatment
 - TEAEs related to IMP leading to discontinuation of study treatment
- TEAEs leading to modification of study treatment
 - TEAEs related to IMP leading to modification of study treatment
- TEAEs leading to study discontinuation
 - o TEAEs related to IMP and leading to study discontinuation
- TEAEs of special interest
 - TEAEs of special interest related to IMP
- TEAEs requiring Adjudication
- TEAE related to Hepatic Encephalopathy (as indicated by the Investigator on the AE CRF page)

The following summaries will be presented by SOC and PT:

- TEAEs
- TEAEs by Maximum CTCAE Grade
- TEAEs related to IMP
- TEAEs related to IMP by Maximum CTCAE Grade
- TEAEs of special interest

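### The 52-week TEAE tables are crude percentages over patients with unequal follow-up, so they understate incidence to Week 56 by an amount the documents do not allow to be fixed

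*SAP*

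**What the plan says.** SAP 10.7.1 defines two safety periods: 24 weeks plus 30 days, and 52 weeks plus 30 days. For the longer one it states "Patients enrolled under protocol version 5.0 will contribute safety data up to Week 28 only", while patients enrolled under versions 1.0 to 4.0 may contribute up to Week 56. It presents this analysis as covering the whole randomized period and as a source of longer-term safety information.

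SAP 10.7.2 gives the matching event definition, which counts events "after initiating the IMP until Week 56 (Week 52 + 30 days").

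SAP 12.6.1 presents the TEAE tables by treatment group and "total for the SS and repeated for both treatment emergent definitions". On the statistic it says: "All AE summaries will include the number and percentage of subjects in each category and the number of events". SAP 9.6.2 fixes the population: "The safety analysis set (SS) will include all randomized subjects who receive at least 1 tablet of IMP or placebo". That set makes no distinction by protocol version.

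Protocol 3.1 adds a special note for patients on the version 4 schedule: those "already beyond Week 24 should permanently discontinue IMP as soon as possible and have an EoT Visit 30 days after their last dose".

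Neither document plans, for adverse events, an exposure-adjusted rate, a time-to-event estimate or a denominator restricted to patients on the 52-week schedule.

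**The concern.** A percentage of patients with an event can be read as incidence over a window only if everyone in the denominator could be observed through that window. That holds for the 24-week tables, where SAP 10.7.1 cuts everyone at the same point. It fails for the 52-week tables. Between about Week 28 and Week 56 the denominator includes patients in whom no event can be recorded. The SAP justifies the Week 56 cut by consistent follow-up for all patients, but that aim cannot be met once version 5.0 patients stop at Week 28.

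The result is a mixture of 28-week and up-to-56-week incidences, weighted by the enrolment mix. A reader who takes it as 52-week incidence will take the absolute risk to be lower than it is. This matters because the 52-week window is the only planned summary that captures later events in the randomized part; under SAP 8.3.3 and 9.6.2, extension data are only listed.

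**Working it through.** **Is there a figure to reproduce?** Not on this point: the documents state no 52-week incidence. The planned size does reproduce: 16 / (1 − 0.25) = 21.3, rounded up to 22 per arm, and 3 × 22 = 66 (SAP 8.1).

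**Inputs from the documents**
- Shorter observation: 24 × 7 + 30 = 198 days (28.3 weeks).
- Longer window: 52 × 7 + 30 = 394 days (56.3 weeks).
- Denominator: not written out as a formula; the Safety Set count is the natural reading of SAP 12.6.1 with 9.6.2.
- Version 5.0 share: not given. SAP 10.11 offers one clue: "Approximately 15 subjects will have no baseline value for the PROMIS-short form-Fatigue 7b Daily as they were enrolled under Protocol Version 1.0". With 60 to 70 patients, the version 5.0 share is therefore at most about 1 − 15/60 = 0.75 to 1 − 15/70 = 0.79. This does not limit the truncated share f, because earlier-version patients who stopped at the amendment are cut off too.
- Event rates and hazard shape: not given.

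**Formula.** If a share f is observed to about Week 28 and the rest to Week 56:
- reported = f × p28 + (1 − f) × p56
- relative understatement = 1 − reported/p56 = f × (1 − p28/p56)

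This is positive whenever f > 0 and some first events occur after Week 28.

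**Illustration with a constant hazard.** p56 = 1 − (1 − p28)^(394/198), with 394/198 = 1.990. For p28 = 10%, p56 = 1 − 0.9^1.990 = 18.9%. With f = 0.50 the table would show 0.5 × 10% + 0.5 × 18.9% = 14.5%, which is 23.6% too low.

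| p28 | p56 | Reported (understatement), f = 0.25 | f = 0.50 | f = 0.75 |
|---|---|---|---|---|
| 5% | 9.7% | 8.5% (12.1%) | 7.4% (24.2%) | 6.2% (36.4%) |
| 10% | 18.9% | 16.7% (11.8%) | 14.5% (23.6%) | 12.2% (35.3%) |
| 30% | 50.8% | 45.6% (10.2%) | 40.4% (20.5%) | 35.2% (30.7%) |

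**How far the assumptions move it**
- Front-loaded onset (Weibull shape 0.3), same f and p28 range: 3.9% to 13.6%.
- Rising hazard (Weibull shape 1.5), same range: 13.1% to 47.0%.
- Very common events (p28 = 90%, constant hazard): 2.3% at f = 0.25 and 6.8% at f = 0.75.
- Version 5.0 share 0.75, with half of the remaining patients also cut at about Week 28: f = 0.75 + 0.25 × 0.5 = 0.875, and at p28 = 5% the understatement is 42.4%. This is a limiting case, since patients stopped after Week 24 may be followed somewhat beyond Week 28.

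**Between arms.** With the same f in each arm, the reported risk difference is D56 − f × (D56 − D28), where D28 and D56 are the true differences to Weeks 28 and 56. The part of a difference that arises after Week 28 is shrunk by the factor 1 − f, but neither arm is systematically favoured.

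**The case against.** The strongest reply is that these are not the main safety tables. The safety objective is set over 24 weeks, SAP 10.7.1 says the 24-week window is the one consistent with the objectives, and protocol 8.1 promises no more than that later data may be summarized where there are enough of them. The SAP also states the Week 28 limit openly. It plans numbers on treatment by time point (12.1), exposure duration by period (12.3.3) and a treatment-emergent flag for each window in the listings (12.6.1). SAP 10.7.1 does not call the 52-week percentages an estimate of 52-week incidence.

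This lowers the weight of the point but does not answer it. Exposure and numbers on treatment appear apart from the event tables and contain no time to first event, so a reader cannot rebuild a rate for a given preferred term or AESI from them.

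Three stronger readings are tempting and are not supported:
- **That the plan understates incidence by a definite 10% to 36%.** That range depends on assumed values of f, p28 and the hazard. Other values the documents allow fall outside it on both sides. A version 5.0 share of 75% also sits at the edge of what SAP 10.11 allows, since it leaves almost no enrolment under versions 3.0 and 4.0.
- **That the comparison between arms is biased.** SAP 8.2 says the randomization scheme was unaffected by version 5.0, so f should be similar across arms. Chance imbalance is possible at about 22 per arm, but that is not a systematic shift.
- **That every earlier-version patient is followed for 394 days.** Protocol 3.1 contradicts this for those stopped at the amendment. SAP 10.7.2 also assigns events from the first extension dose onward to the Extension Phase, which leaves the end of the window unclear for extension entrants.

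**Conclusion.** The point holds for the 52-week TEAE, TESAE and AESI tables. As specified, they are crude percentages with unequal planned follow-up, and they lie below incidence to Week 56 whenever any first events occur after Week 28. The direction follows from the text, given the natural reading that the denominator is the Safety Set. The size is f × (1 − p28/p56) and cannot be computed from the documents. The range of 10% to 36% is an illustration and not a bound: roughly 4% to 47% results from changing only the hazard shape over the same f and p28, with smaller values still for very common events.

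The damage is to absolute incidence and to how clearly late differences show. The 24-week tables, which carry the stated safety objective, are unaffected. The change should be made because it is cheap and the table would otherwise be misread, but it does not touch the primary analysis.

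**What to change.** In SAP 12.6.1, for the 52-week TEAE, TESAE and AESI tables, add one of the following:
- patients with at least one event per 100 patient-years at risk, counting time from first dose to first event or to the end of that patient's own observation window;
- a cumulative incidence estimate that censors each patient at the end of that window;
- events with onset after Week 28, as a percentage of patients still observed after Week 28.

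Whichever is chosen, state the number of patients at risk after Week 28 by arm, and define the end of the observation window for version 5.0 patients, for patients stopped at the amendment and for extension entrants. Keep the crude percentages for the 24-week tables.

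The cost is SAP wording and modest programming from dates already collected, plus one more column in the 52-week tables. A patient-year rate assumes a roughly constant hazard and should carry that caveat. The other two options avoid the assumption, but will be imprecise because the SAP itself (12.5.4) expects few patients beyond Week 24.

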8.2 Randomization

The randomization schema remains unaffected by Protocol Amendment version 5.0. Eligible subjects enrolled according to Protocol Amendment version 5.0 will be randomly assigned to oral setanaxib 1200 mg/day, 1600 mg/day, or placebo, according to a 1:1:1 randomization ratio, stratified by Screening serum ALP < or ≥3.0×ULN.

Randomization will be performed via a centralized Interactive Web Response System (IXRS) contracted through Almac. At registration, the IXRS will assign a unique subject identification number that will be used on all of the subject's eCRFs and serious adverse event (SAE) report forms. If a subject is rescreened (see Protocol Amendment version 5.0 Section 4.3), the rescreened subject should be assigned a new unique screening number.

Any subjects who entered the Extension Phase under protocol versions 1.0 to 4.0 will have received the same setanaxib treatment dose they received during the first 52 weeks of study treatment (the Main Part). Subjects initially randomized to placebo will have been switched to setanaxib 1200 mg/day or 1600 mg/day according to a 1:1 randomization ratio in the Extension Phase. Randomization in the Extension Phase was not stratified. All subjects will have had a new randomization number assigned on enrollment into the Extension Phase, even if they were not re-randomized to a new treatment arm; this is to protect the blind for subjects prior to the completion of the double- part of the study.

During the course of the study, the statistician and the programmers supporting the IDMC analysis will be unblinded and will remain separate from the wider project team throughout the life of the study. The randomization will be performed by the external IXRS provider, Almac. The blinded statistician supporting the study will have no access to the unblinded randomization schedule. The Investigator, the site personnel,

Version Date: 27-June-2024 Sponsor: Calliditas Therapeutics Suisse SA

Protocol No: GSN000350

the Sponsor and their representatives involved in monitoring and conducting the study, the Adjudication Committee, and the subjects will be blinded to treatment assignments until the study is unblinded for the primary analysis. For full details refer to the Data Blinding and Documentation plan.

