Evaluation of drug-induced serious hepatotoxicity (eDISH) analysis will be conducted in order to explore potential liver toxicity signals by treatment group. A eDISH plot will be produced, which will display for each subject during the treatment period the maximal total ALT/AST value (expressed as a multiple of the ULN) against the maximal Total Bilirubin value (expressed multiple of the ULN) to identify possible values above Hy's law range. The plot will be produced using the SS and treatment period of 52 weeks (Section 10.7.1) and will display the maximal on-treatment value of ALT/AST and total bilirubin.

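### The SAP ends the 52-week safety period of Extension Phase entrants at Week 56, not at the first extension dose, and does not settle whether crossed-over placebo patients' first weeks on setanaxib count as placebo

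*SAP*

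**What the plan says.** SAP 10.7.1 defines a 24-week and a 52-week safety period, each with 30 days added. In the 52-week period, for version 1.0 to 4.0 patients "who entered the extension phase, the safety data will be cut at Week 56 (Week 52 + 30 days". It adds: "This approach will be applied to other safety endpoints". SAP 10.7.2(2) sets the matching limit for adverse events: for extension entrants, "the AEs that occur, or have worsened in severity or seriousness after Week 56 (Week 52 + 30 days) will NOT be taken into consideration".

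Three further rules decide what those 30 days contain and where they are shown.

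- SAP 8.2: "Subjects initially randomized to placebo will have been switched to setanaxib 1200 mg/day or 1600 mg/day" on entering the Extension Phase.
- SAP 10.4: for entrants, the last dose of the randomized part "will be the day prior to the date of the first dose of IMP in the Extension Phase".
- SAP 9.6.2: "Subjects included will be analyzed based on actual treatment initially received".

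Other passages point the other way.

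- The closing rule of 10.7.2 sends such events to the extension instead (the quote stops just before that phase is named): "If the start date of the TEAE is on or after the first dose in the Extension Phase, the TEAE will be assigned to the".
- 8.3.3 and 9.6.2 confine extension data to listings.
- 10.5 gives crossed-over placebo patients an active actual arm in the extension.
- 12.6.3 handles extension laboratory data against an extension baseline.
- 12.6.6 lists extension ECG intervals.

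**The concern.** For a patient who stops at Week 52, the added 30 days are off-drug follow-up. For a placebo patient who enters the extension, they are the first month on setanaxib. If those days stay under placebo, drug-exposed events and laboratory peaks are added to the comparator. That would tend to mask a drug effect, in a display that 10.7.1 describes as covering the whole randomized period.

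Some outputs are specified for the 52-week period only: the eDISH plot (12.6.4), vital signs (12.6.5), and the ECG categories and physical examination (12.6.6). They have no separate 24-week version to fall back on. The eDISH plot is the most sensitive, because it shows each patient's maximum and one post-crossover value could set a placebo patient's point. Liver safety is a live question here: protocol 1.1.4 reports four liver-test SAEs in this study considered possibly related to study drug.

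**Working it through.** **1. The stated cut.** 52 × 7 + 30 = 394 days, and 394 / 7 = 56.3 weeks, which agrees with Week 56. The 24-week period gives 24 × 7 + 30 = 198 days, or 28.3 weeks, which agrees with Week 28. That is well before any crossover.

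**2. Days on setanaxib before the cut.** By 10.4 there is no gap between the two parts. If the first extension dose is on study day s, the overlap is 394 − s + 1 days. The documents do not give s. Day 365 is the Week 52 target in the SAP's window table, and the range around it is an assumption.

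| First extension dose (s) | Overlap, days | Share of 394 days |
|---|---|---|
| 351 | 44 | 11.2% |
| 358 | 37 | 9.4% |
| 365 | 30 | 7.6% |
| 372 | 23 | 5.8% |
| 379 | 16 | 4.1% |

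Counting the 30 days from the Day 365 target would put the cut at Day 395 and add one day to each overlap. Ending the period on the day before the first extension dose makes every overlap 0.

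**3. Adverse events.** Take a placebo patient with a first extension dose on Day 365 and a new event on Day 380.

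- By 10.7.2(2) the event precedes Week 56, so it is a 52-week TEAE. By 9.6.2 it is tabulated under placebo.
- By the last rule of 10.7.2 it belongs to the Extension Phase. By 8.3.3 it is listed only.
- 12.6.1 tabulates TEAEs as defined in 10.7.2 and flags extension-assigned events in the listings. It does not say that they leave the tables.

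Two programmers could therefore build different placebo columns from the same text.

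**4. Other safety data.** There is no start-date assignment rule here; 10.7.1 carries the Week 56 cut across. For worst-case summaries, 10.3 takes all post-baseline values in the period, unscheduled ones included. For eDISH, "The plot will be produced using the SS and treatment period of 52 weeks (Section 10.7.1".

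The first extension analysis visit after Extension Baseline is targeted at extension Day 113, well beyond a 30-day overlap. Exposure is therefore probably mainly through unscheduled values entering worst-case summaries and eDISH maxima.

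**5. Visit window.** The Week 52 window stays open to Day 460, which is 460 − 365 = 95 days past its target. With s = 365, Day 460 is extension Day 460 − 365 + 1 = 96. The Week 16 Extension window opens at extension Day 2, so both windows claim extension Days 2 to 96.

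**6. Exposure.** The note in 10.7.1 cuts exposure at Week 52 without the 30 days. Events would then be counted over a longer period than the exposure reported beside them.

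**The case against.** The strongest case against is that the SAP already excludes these data. The phase-assignment rule closes the same section that sets the Week 56 limit. The listings-only statements in 8.3.3 and 9.6.2 cover every type of safety data. Section 10.5 relabels the patients as active. Section 12.6.3 restricts extension laboratory data and changes their baseline, and 12.6.6 lists extension ECG intervals. The eDISH plot is described as showing on-treatment maxima, which could be read as ending with the randomized part. The display at issue is supplementary, because the safety objective covers 24 weeks.

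Much of this stands. A reader might infer that crossover data are definitely counted as placebo, or that nothing in the SAP removes post-crossover laboratory values. The documents support neither statement.

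The passages still do not resolve the matter. None is said to override the Week 56 cut. If they all did, the bullet in 10.7.1 written specifically for extension entrants would have almost no function, since all their time after the last randomized dose is extension time. The phase-assignment rule covers TEAEs only. The listing sentence in 9.6.2 refers to subjects who entered the extension rather than to a period, so taken literally it would also remove their first 52 weeks. The on-treatment wording for eDISH sits beside an explicit reference to the 52-week period in 10.7.1.

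It is also fair that patients already on setanaxib kept their dose (8.2), so their data after Week 52 are not misattributed.

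**Conclusion.** The SAP contains an unresolved contradiction. Its specific rule, applied literally, places about the first month on setanaxib of crossed-over placebo patients in the placebo column of the 52-week tables and the eDISH plot. Other passages point to exclusion, and no order of precedence is given. The overlap is 30 days per such patient if the extension starts on Day 365, and 16 to 44 days for an assumed two-week shift either way.

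The number of crossovers is not stated and may be zero, so the effect on placebo incidence cannot be computed. For scale only: on the planned 22 patients per arm, one patient whose sole qualifying event fell in that window would move the placebo incidence by 1/22 = 4.5 percentage points. A reader might infer that the placebo rate is raised and a drug effect hidden. That is a possible result, and the documents do not establish it.

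The 24-week safety tables, which end at Week 28, and primary efficacy at Week 24 are unaffected. The text should be corrected because the change is small and some safety outputs exist only for the 52-week period.

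**What to change.** In SAP 10.7.1 and 10.7.2(2), state that for all extension entrants the 52-week safety period ends at the earlier of Week 56 and the day before the first Extension Phase dose. Apply this to adverse events and to all other safety endpoints, including eDISH. Apply it in every arm, so that follow-up stays symmetric. Data from the first extension dose onward appear only in the extension listings.

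Then align the related text. In 9.6.2, refer to data collected during the extension rather than to subjects who entered it. In 12.6, say that extension-assigned events and values leave the 52-week summaries. Close the Week 52 analysis window, now open to Day 460, at the same date for these patients.

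The cost is a short SAP revision and one date condition in programming. The downside is that extension entrants have no 30-day tail in the 52-week tables, including those who stayed on the same setanaxib dose and whose data were not misattributed.
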